2.3 Clinical Experience with P-321 Ophthalmic Solution

There has been one study completed with P-321 Ophthalmic Solution in which 40 subjects with mild to moderate dry eye disease were treated with P-321 Ophthalmic Solution. In this study, P-321 Ophthalmic Solution was well-tolerated at concentrations of 0.0005%, 0.0015%, 0.005% instilled twice daily for up to 15 days and 0.01% instilled twice daily for up to 28 days. There were no clinically relevant adverse drug-related, dose-related or time of treatment-related effects on any safety measure. No serious adverse events (SAEs) were reported. No evidence of systemic exposure of P-321 was observed.

Although this study was not powered for effects on efficacy measurements, improvements in the frequency and severity of symptoms of dry eye disease that approached statistical significance compared with placebo were observed. In addition, consistent with the proposed mechanism of action of P-321, the treatment difference relative to placebo favored P-321 for the measurements of tear meniscus height (TMH) observed in this study.

2.4 Justification for Route of Administration and Dose Selection

P-321 Ophthalmic Solution is expected to exert its biological activity through direct interaction with ENaC on the corneal and conjunctival surface of the eye. Since the intended route of administration for P-321 is topical ocular, this route of administration will be used in this study. The dose planned for this study was selected based upon results of the first clinical study and preclinical safety studies.

This study is a single day crossover comparing P-321 Ophthalmic Solution and Placebo on the pharmacodynamic measure, tear volume. During Phase 1, a single dose of 0.017% will be administered and during Phase 2 and based on the recommendation of the Data Review Group, a single dose of either 0.05%, 0.017% or 0.01% will be administered. These doses on a single instillation frequency and are covered by the safety profile obtained in the most sensitive species (dog) with safety margins that range from 6-fold to 1.2-fold.

2.5 GCP Compliance

This clinical trial will be conducted in compliance with the protocol, International Conference on Harmonization (ICH) Good Clinical Practice guidelines, and other applicable regulatory requirements.

2.6 Population to be Studied

Dry eye disease is a multifactorial debilitating disease of the ocular surface characterized by ocular signs of corneal and conjunctival impairment and damage of the protective epithelial surface, as well as, decreased tear volume, decreased tear break-up time, and symptoms of discomfort that can range from mild to severe such as, burning, pain, stinging, itching, swelling, foreign body sensation, photophobia, and ocular fatigue. Frequent instillation of artificial tears is currently the most commonly used treatment for mild to moderate dry eye signs and symptoms.

According to recent prevalence estimates, dry eye disease can affect up to 20 million people in the US, with a disproportionate number of women and elderly being afflicted. However, with the spread use of digital technologies in recent years, increased incidence of dry eye in younger adults is being observed. There is a heterogeneous collection of diseases with many shared characteristics that can precipitate dry eye disease. Dry eye disease is one of the hallmarks of the Sjögren's syndrome (SS); however, they represent only a fraction of subjects who experience dry eye symptoms. Dry eye is also observed in approximately 40 to 60% of subjects who have undergone hematopoietic stem cell transplantation and develop graft versus host disease ([Saboo, 2015](#)). One core abnormality of the disease is the decrease in tear volume that can be originated by a deficiency of tear secretion or composition which in turn triggers the loss of volume and compromises the protective barrier of the ocular film. Additionally, dry eye symptoms can be the side effect of many commonly used medications such as anticholinergics, antidepressants, and environmental factors such as air conditioning and focusing on video displays for prolonged periods of time. These symptoms of dry eye can vary from mild to severe and in the most severe cases, can result in significant vision impairment and permanent damage of the ocular surface. In this study, subjects with tear deficient dry eye disease will be recruited for participation.

Approximately 24 subjects with tear deficient dry eye disease documented by low tear volume as measured by UHR-OCT will be completed in this single-center, randomized, cross-over, placebo controlled study to evaluate the changes in tear volume by P-321 Ophthalmic Solution or Placebo. The study consists of two Phases. Approximately 8 subjects participating in Phase 1 will receive 0.017% P-321 Ophthalmic Solution or Placebo, and the remainder of the 24 subjects participating in Phase 2 will receive either 0.05%, 0.017% or 0.01%. The decision on the dose administered in Phase 2 will be made following unmasked data review from subjects in Phase 1. In each Phase, subjects will receive sequentially two treatments: P-321 Ophthalmic Solution (Treatment A) and Placebo (Treatment B). Subjects will be randomly assigned to receive treatment sequence AB or BA, with each subject in Phase 1 and Phase 2 being treated with P-321 Ophthalmic Solution and placebo. The Principal Investigator, Medical Monitor and Parion Sciences representatives not involved in the day to day conduct of the study will review unmasked data as part of the Data Review Group, which will decide the dose to be used in Phase 2 of the study. The treatment assignments will remain masked to subjects in the study, the clinical monitor, and other site and Parion Sciences personnel involved in the conduct of the study and not involved in the Data Review Group. Additional unmasked reviews of subject data may occur during the study to make recommendations on further dose adjustments and for planning purposes. These reviews will follow the procedures outlined above.

3 TRIAL OBJECTIVES AND PURPOSE

The primary objective of this trial is to assess changes in tear volume by the non-invasive techniques Ultra High Resolution Optical Coherence Tomography (UHR-OCT) following the administration of P-321 Ophthalmic Solution or Placebo in subjects with tear deficient dry eye disease.

The secondary objectives are to:

- assess changes in lower tear meniscus height by Keratograph 5M
- compare lower tear meniscus height measurements between UHR-OCT and Keratograph 5M
- assess the duration of action of P-321 Ophthalmic Solution
- compare the pharmacodynamic activity of different strengths of P-321 in subjects with tear-deficient dry eye
- monitor safety and tolerability of P-321 Ophthalmic Solution

4 INVESTIGATIONAL PLAN

4.1 Overall Study Design

This is a single-center, randomized, cross-over, placebo-controlled, Phase 2a trial designed to evaluate the pharmacodynamic effects of tear volume of P-321 Ophthalmic Solution in tear-deficient dry eye subjects. Approximately 24 eligible subjects will complete the study which consists of two Phases: Approximately 8 subjects participating in Phase 1 will receive 0.017% P-321 ophthalmic Solution and Placebo, and the remainder of the 24 subjects participating in Phase 2 will receive either 0.05%, 0.017% or 0.01% P-321 and placebo. The decision on the dose administered in Phase 2 will be made following unmasked data review from subjects in Phase 1. In each Phase, subjects will receive sequentially two treatments: P-321 Ophthalmic Solution (Treatment A) and Placebo (Treatment B). Subjects will be randomly assigned to receive treatment sequence AB or BA, in a 1:1 ratio.

The pharmacodynamic measures of tear volume will be assessed by two methods: UHR-OCT and Keratograph 5M. Optical coherence tomography (OCT) has been used to image the anterior segment of the eye including tears on the ocular surface. The method is non-invasive and non-contact which is suitable for imaging the tear meniscus around both upper and lower lids. The system at Bascom Palmer Eye Institute is a custom made OCT system (UHR-OCT) with an ultra-high resolution (3 μ m). Many previous studies have been done using UHR-OCT and its clinical application has been well documented. With the wide scan of the UHR-OCT, cross-sectional images of the tear menisci can be imaged and tear meniscus volume can be calculated. The Keratograph 5M is a corneal topographer with a built in camera optimized for external imaging. The Keratograph 5M has a feature that enables the non-invasive assessment of the tear meniscus height of the inferior eyelid from high resolution images obtained under infrared light. With the use of a built-in measurement tool the height of the tear meniscus is obtained.

The study will consist of three study visits: a Screening Visit (Visit 1), and two treatment visits (Visit 2 and Visit 3). The duration of the study may be up to 23 days.

At Visit 1, three tear volume measurements will be conducted over 1 hour with measurements taken approximately 30 minutes apart (initial timepoint, and at 30 and 60 minutes later) and prior to any invasive ocular assessments. The average of these three measurements will be obtained and used as baseline tear volume and meniscus height and to determine the eligibility of the subject to participate in the study.

At Visits 2 and 3, tear volume will be assessed serially over 6 hours: Before administration of assigned study medication (time = 0, pretreatment), and at 15 minutes, 30 minutes, 1 hour, 2 hours, 4 hours and 6 hours after study medication administration. Subjects will be asked to arrive to the clinic for Visit 2 and Visit 3 between 8:00AM and 11:00AM and at approximately the same time as Visit 1.

Safety assessments including adverse events (AEs), biomicroscopy and external eye examination and an assessment of comfort immediately after taking the medication will be conducted following each in-clinic dose. Changes in medical conditions and medication, abbreviated physical exam changes and vital signs will be recorded periodically throughout the study. A post

[figure not shown]
instillation dry eye symptom assessment will be conducted at Visits 2 and 3 immediately prior to the 2 hour post dose time point.

Subjects may be asked to stop or withhold certain medications, and on visit days and for at least 6 hours after dosing with study medication, withhold certain medications and not wear contact lenses on visit days. After the assessments of Visit 3 are completed, the subject will be discharged from the study.

A detailed schedule of the time and events for the study is provided in [Appendix I](#).

A schematic of the study design is shown in [Figure 1](#).

Figure 1: P-321-201 Study Schematic

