5 SELECTION AND WITHDRAWAL OF SUBJECTS

5.1 Subject Inclusion Criteria

Subjects must meet the following criteria at Screening to be enrolled in the study:

1. Provide written informed consent
2. Male or female subjects aged 18 to 80 years
3. Are willing and able to follow instructions and can be present for the required study visits for the duration of the study
4. Have a history of predominantly tear-deficient dry eye of mild to moderate severity, in both eyes, supported by a previous clinical diagnosis
5. Subjects must have in at least one eye an average tear meniscus height (TMH) of the lower eye lid of 210 μm or less as assessed by UHR-OCT
6. Have normal lid anatomy
7. Female subjects of child bearing potential must have a negative serum pregnancy test at Screening and agree to use a medically acceptable form of birth control (e.g., intrauterine device, birth control pill, patch or subcutaneous implant, condoms, diaphragm, or abstinence) throughout the duration of the study. Females who are breast feeding an infant are not eligible to participate in the study.
8. Subjects must:
 - a. Remain on current medications for the duration of the study
 - b. Be on the current medication regimen at least during the past 28 days
 - c. Be able to withhold ocular topical medications, including artificial tears, topical steroids, Restasis[®], Xiidra[®], autologous serum, and lid wipes and scrubs on visit days while in the clinic, and for at least 6 hours after dosing with study medication
 - d. If they are contact lens wearers, be able to withhold wearing contact lenses on visit days, while in the clinic, and for at least 6 hours after dosing

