5.4 Study Eye

The Study eye will be the eye that meets entry criteria as defined in [Section 5.1](#), [Section 5.2](#), and [Section 5.3](#). If both eyes meet entry criteria, the study eye will be the eye with the lower average TMH by OCT. If both eyes have the same average TMH, then the qualifying study eye will be the **right eye**.

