6.4 Early Termination Visit

The following assessments will be performed at the Early Termination Visit for randomized subjects who are withdrawn from the study prematurely:

- Assess adverse events since the last visit and during this visit
- Assess concomitant medications and medical changes since last visit
- Collect vital signs (pulse, blood pressure, temperature and respiration rate) and height and weight
- Conduct an abbreviated physical examination (including respiratory, cardiovascular, musculoskeletal, gastrointestinal, and dermatological)
- Conduct a biomicroscopy and external eye examination

6.5 Selecting Dosage Strength in Phase 2

The decision of dose strength for P-321 Ophthalmic Solution in Phase 2 of the study will be the responsibility of the Data Review Group constituted by the Principal Investigator (or a designee not directly involved in the conduct of the study), the Medical Monitor and representatives of Parion Sciences. Decision on the dose level to be given in Phase 2 will be made based on unmasked review of the study data from the first 8 subjects by the review committee. Data to be considered will include safety and efficacy measures. A detailed criterion for Dose selection for Phase 2 is described in [Appendix XIV](#) and outlined below.

The dose level may be increased to 0.05% in Phase 2 in the event that:

- 1) No cases of serious, suspected related, unexpected events are noted in Phase 1 OR
- 2) No cases of serious ocular safety events are noted in Phase 1
- 3) Lack of evidence that P-321 produced an increase in tear volume based on OCT and/or Keratograph 5M, or evidence that additional improvements in tear volume (or the duration of effect) may be obtained with a higher dose.

The dose level may be decreased to 0.01% in Phase 2 in the event that:

- 1) No cases of serious, suspected related, unexpected events are noted in Phase 1
- 2) No cases of serious ocular safety events are noted in Phase 1
- 3) There is evidence of a significant increase in tear volume and the duration of effect based on OCT and/or Keratograph 5M

The dose level may remain at 0.017% (the same as in Phase 1) in the event:

- 1) No cases of serious, suspected related, unexpected events are noted in Phase 1
- 2) No cases of serious ocular safety events are noted in Phase 1
- 3) There is not compelling data to either increase or decrease the strength for Phase 2.

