8.1.2 Pharmacodynamic parameters

UHR-OCT will assess the following parameters in both eyes: UTMH, LTMH, UTMV, LTMV, and TTMV (UTMV + LTMV). Treatment group differences for tear volume assessments will be conducted via comparisons of tear meniscus height, and if applicable, tear meniscus volume (TMV). These parameters will be compared between each dose of P-321 Ophthalmic Solution and Placebo using a t-test for study eyes, and for all eligible eyes. Analysis of covariance (ANCOVA) models will be used to adjust for the baseline TMH and TMV for study eyes. For all eligible eyes, a generalized estimation equations (GEE) will also be used to account for the correlation between eyes. For the GEE analysis, an exchangeable correlation matrix will be assumedArea under the curve (AUC) analysis will also be performed as an exploratory analysis to compare OCT assessments and Keratograph 5M LTMH for Placebo vs each dose of P-321.

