8.2 Sample Size Estimation

An initial sample size of approximately 24 subjects is proposed for this study. The study design includes OCT measurements at time 0 (pretreatment) and post dose at 15 minutes, 30 minutes, 1 hour, 2 hours, 4 hours and 6 hours. Shen et al. ([Shen, 2009](#)) reported that among the measures of tear volume and tear film thickness obtainable through OCT, the most sensitive and specific measure of dry eye is the low tear meniscus height (LTMH). Power estimations for a two-period, two-treatment, two-sequence crossover design (2x2x2), this study size when all subjects treated with P-321 are analyzed, will provide 98% power to detect a difference of 60 μm at 1 hour or a power of 99% if the average increase in LTMH over the six hours is 60 μm (assuming within-subject SD of 71). In this study it is expected that the drug will reach its peak effect at 1 hour post dose and that the effect diminishes at hours 4 and 6 (to values still above pre-dose values).

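### The only defined baseline is the Visit 1 screening mean, which cancels from the crossover contrast and builds regression to the mean into within-treatment change; the pre-dose value has no analysis role

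*Combined protocol and SAP*

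**What the plan says.** Section 4.1 contains the only definition of baseline for the tear measures, the mean of three Visit 1 readings: "The average of these three measurements will be obtained and used as baseline tear volume and meniscus height and to determine the eligibility". That mean is compared with the 210 µm limit in Section 5.1 ("Subjects must have in at least one eye an average tear meniscus height (TMH) of the lower eye lid"). When both eyes qualify, Section 5.4 uses it again: "the study eye will be the eye with the lower average TMH by OCT". Section 5.3 exempts the limit from rechecking at Visits 2 and 3.

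At each treatment visit the measurement times are: "Before administration of assigned study medication (time = 0, pretreatment), and at 15 minutes, 30 minutes, 1 hour, 2 hours, 4 hours and 6 hours". The first of these is labelled pretreatment, not baseline.

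Section 8.1.2 then states: "Analysis of covariance (ANCOVA) models will be used to adjust for the baseline TMH and TMV for study eyes". It does not redefine baseline. The primary endpoint in Section 4.2.1 is a change over time with no named reference value. Section 8.2 does use the pre-dose value as a reference, but only as a planning expectation: "the effect diminishes at hours 4 and 6 (to values still above pre-dose values". For one of the Phase 2 strength options, Section 6.5 gives this criterion: "There is evidence of a significant increase in tear volume and the duration of effect based on OCT and/or Keratograph 5M". It does not say what the increase is measured against.

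**The concern.** Read literally, the ANCOVA covariate and any change from baseline both use Visit 1. Two things follow.

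- **Precision.** The study is powered as a 2x2 crossover. A covariate with one value per subject cannot sharpen a within-subject contrast. The time-0 value differs between a subject's periods and can, but the plan gives it no such use.
- **Regression to the mean.** Visit 1 selects the subject and the eye, and is taken 3 to 23 days before dosing (3–9 days to Visit 2, then 7–14 more to Visit 3). Change from it will tend to be upward under either treatment. This threatens readings made within one treatment: the time course on P-321, duration of action judged as return to baseline, and a Phase 1 review of about 8 subjects that looks at P-321 alone.

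**Working it through.** **Inputs from the documents.** N about 24, difference 60 µm, SD 71 labelled within-subject, stated power 98% at 1 hour (Section 8.2); alpha 0.05 (Section 8.3; two-sided assumed); about 8 subjects in Phase 1, leaving about 16.

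**Not in the documents.** Variance components, and rho, the correlation between the period differences in pre-dose and post-dose values. All results below are therefore ranges.

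**1. The plan's own power (noncentral t, df = N − 2 = 22).**
- 71 as SD of the paired difference: SE = 71/√24 = 14.49; 60/14.49 = 4.14; power 97.7%. This reproduces 98%.
- 71 as within-subject SD, as labelled: SE = 71·√(2/24) = 20.50; 60/20.50 = 2.93; power 79.9%.

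Both readings are carried forward.

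**2. Why Visit 1 cancels.** Let subject i have Visit 1 value x_i and outcomes y_i1 and y_i2. The covariate's contribution to y_i1 − y_i2 is β(x_i − x_i) = 0. In one simulated trial of 24 complete pairs with fixed subject effects, the estimate was 48.92 and the SE 16.75 in three analyses: without Visit 1, with it as covariate, and as change from it.

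**3. Gain from the time-0 covariate.** SE becomes SE·√(1 − rho²), df = N − 3. Example: 71 as labelled, N = 24, rho = 0.5 gives 20.50·√0.75 = 17.75; 60/17.75 = 3.38; power 89.7%.

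| Reading of 71 | N | No covariate | rho 0.3 | rho 0.5 | rho 0.7 |
|---|---|---|---|---|---|
| SD of difference | 24 | 97.7% | 98.5% | 99.5% | >99.9% |
| SD of difference | 16 | 88.1% | 90.5% | 95.0% | 99.2% |
| Within-subject SD | 24 | 79.9% | 83.3% | 89.7% | 97.4% |
| Within-subject SD | 16 | 60.4% | 64.0% | 72.3% | 87.1% |

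At N = 8 and rho = 0.14 the lost degree of freedom outweighs the gain: 51.8% to 49.6%, or 29.7% to 28.5%.

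**4. Same variance components throughout, N = 24.** With rho = day²/(day² + measurement²):

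| Day SD / measurement SD | rho | No covariate | With time 0 |
|---|---|---|---|
| 20/30 | 0.31 | >99.9% | >99.9% |
| 20/50 | 0.14 | 95.8% | 96.0% |
| 50/30 | 0.74 | 92.6% | 99.9% |
| 50/50 | 0.50 | 80.2% | 89.9% |

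**5. Plain change from time 0 is not the remedy.** Its SE is SE·√(2 − 2·rho), larger than the post-dose SE whenever rho is below 0.5. At rho = 0.3 and N = 24, power falls from 97.7% to 91.7%, or from 79.9% to 65.7%.

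**6. Regression to the mean.** Simulation with no drug effect, 400,000 subjects in each of 24 scenarios. Assumed: population mean LTMH 200, 230 or 260 µm; between-subject SD 50; between-eye SD 20; day SD 20 or 50; measurement SD 30 or 50; day effect shared by the eyes or independent. Visit 1 is the mean of three readings, the lower eye is taken, and 210 µm or less is required.
- Mean post-dose value minus Visit 1: +12 to +62 µm within each treatment.
- P-321 minus placebo: at most 0.4 µm from zero, which is simulation error.
- Sets of 8 in which a one-sample t-test on P-321 alone shows a rise from Visit 1 (upper 2.5% tail): about 10% to 48%.
- The same share for change from that visit's time 0, or for P-321 against placebo: 2.3% to 2.7%.

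A separate simulation (mean 180–250 µm, between-subject SD 60, between-eye correlation 0.7, within-subject SD 50 or 71) gave +14 to +69 µm.

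**The case against.** The main comparison is unharmed, and no section says that change, duration or the Phase 1 review is measured from Visit 1. Sections 6.2, 6.3, 8.2 and 9 all speak of readings before dosing, so a sensible analyst might use time 0 anyway. Section 6.5 specifies no one-sample test, and every Phase 1 subject also has a placebo period. This stands as a limit: the 10%–48% figure describes a reading the text permits, not one it prescribes. None of those sections gives the pre-dose value an analysis role, however.

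The upper figures depend on assumed components, and the 20/30 and 50/30 pairs match neither reading of 71. This also stands. The 20/50 pair, nearest the stated power, gives about 22–33 µm and roughly 13%–27%, with almost no power gain. The 50/50 pair, nearest the SD as labelled, gives about 36–61 µm and 18%–44%.

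The no-precision argument presumes a within-subject model, and Section 8.1.2 names neither pairing nor a subject term. In an unpaired ANCOVA, Visit 1 would lower the reported SE. In the simulated trial a mixed model's reported SE also fell, from 16.75 to 14.29. The estimate did not move, and in further simulations such drops appeared when the subject variance was estimated at or near zero. They are not a real gain in a crossover with complete pairs.

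Section 8.1.3 disclaims formal efficacy endpoints. The planned tests and the power statement are still there to be done well.

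**Conclusion.** The concern holds and should be addressed. The only defined baseline is a value that cannot improve the within-subject comparison and that carries selection into any change measured from it, while a better reference is already collected at each treatment visit.

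The treatment contrast is unbiased either way. The precision forgone runs from negligible (low rho, or the reading that reproduces 98%) to about 3 to 18 power points at N = 24 with 71 as labelled and rho 0.3 to 0.7. Regression to the mean of 12–62 µm is as large as the planned effect at its upper end, but matters only for within-treatment readings against Visit 1. A review that uses the placebo period or the pre-dose value is unaffected.

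**What to change.** State in Sections 4.1 and 8.1.2:

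- For Visits 2 and 3, baseline is that visit's time-0 UHR-OCT value.
- P-321 versus placebo is analysed by a within-subject crossover ANCOVA of the post-dose value with subject, period and treatment, and the period-specific time-0 value as covariate. Add the subject-mean time-0 value if subject is random.
- Time 0 is the reference for descriptive within-period change and duration of action.
- The Visit 1 mean is kept for eligibility, study-eye choice and description at entry. Whether it also helps a between-subject comparison of strengths is a separate choice to state.
- The Phase 1 review shows P-321 minus placebo beside any change within P-321.

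Do not replace the ANCOVA with an unadjusted change from time 0.

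Cost: two or three sentences and one degree of freedom, negligible at N = 16–24 and worth 1–2 power points at N = 8 if rho is low. No new data are needed.
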